The primary efficacy endpoints of the study are adjudicated CV death and HF events (hospitalisation for HF or urgent HF visit). The rationale for selecting CV death over all-cause death is the expectation that HF treatment will decrease CV death and not all potential causes of death (Zannad et al 2014). Heart failure events include both HF hospitalisations and unplanned HF visits requiring urgent treatment independently of whether the exacerbation of HF results in hospitalisation (according to CDISC definitions; Hicks et al 2014; Hicks et al 2018). These are the same endpoint definitions currently employed in the Sponsor's HFrEF outcome study (Dapa-HF; Study D1699C00001).

¹ Left Atrial Enlargement defined by at least 1 of the following: LA width (diameter) ≥ 3.8 cm or LA length ≥ 5.0 cm or LA area ≥ 20 cm² or LA volume ≥ 55 mL or LA volume index ≥ 29 mL/m

² Left Ventricular Hypertrophy defined by septal thickness or posterior wall thickness ≥ 1.1 cm

The rationale for including outpatient HF events, in addition to hospital admissions, is that it is the occurrence of worsening of the patient's condition necessitating treatment, and not the place of treatment, that is important. As stated in EMA Guidance 2016, '...patient are often managed for episodes of transient decompensation or worsening HF in outpatient settings (eg, emergency departments, observation units, other outpatient settings). The capture of events of worsening HF without hospitalisation may be warranted as an additional endpoint.' Including only hospital admissions is likely to overlook a modest but significant proportion of episodes of worsening HF (Skali et al 2014, Okumura et al 2016, Greene et al 2018).

While CV death and HF hospitalisations are clearly important to patients and health-care systems, the impact of HF on patients' symptoms and physical/social functioning is also important. In order to evaluate the treatment effects on these aspects of the impact of HF, we will use the Kansas City Cardiomyopathy Questionnaire (KCCQ), a disease-specific patient reported outcomes (PRO) measure developed for patients with chronic HF. The KCCQ has shown to be a valid, reliable and responsive measure for patients with HF (Greene et al 2018, Spertus et al 2005).

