8.3.2 Efficacy event adjudication

A Clinical Events Adjudication (CEA) Committee will be established for this trial and adjudicate primary efficacy events in accordance with adjudication criteria detailed in the CEA charter.

Events to be adjudicated include components of the primary efficacy endpoint: deaths, hospitalisation for HF, and urgent HF visits. All deaths will be adjudicated to determine if they are CV or non-CV deaths. All adjudication will be done on an ongoing basis throughout the trial.

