The event rate assumptions are based on sub analyses of the TOPCAT and I-PRESERVE studies by geographic region, NT-proBNP levels, prior hospitalisation for HF, and T2D status ([Pfeffer et al 2015](#), [Kristensen et al 2015](#), [Kristensen et al 2017](#)). The original sample size calculation (~ 4700 randomized patients) built on the assumption of an annual event rate of 9% in the placebo group for the majority of prevalent HFpEF patients, importantly all with NT -proBNP ≥ 300 pg/ml by inclusion criterion. Additionally, a subgroup of patients due to be discharged or recently discharged from a HF hospitalisation (here denoted ‘subacute’ patients) with a higher event rate is planned to be included. Assuming 20% of patients from the subacute category with an annual event rate of 24% during the first year and 9% thereafter for the remainder of the study, the original sample size of 4700 patients was estimated to provide the required number of 844 patients with a primary event during a recruitment period of 18 months and a minimum follow-up period of 15 months.

Based on the ongoing blinded monitoring of event accrual (including the percentage of patients from the subacute category), the sample size is increased from original 4700 to approximately 6100 randomised patients. Accordingly, the recruitment period is anticipated to increase from the original 18 months to 26 months. Recruitment might be marginally prolonged in a few countries to meet local targets. The study is event driven and the number of patients or duration may further change.

With the same event rate assumptions as above, assuming 11% of patients from the subacute category, approximately 6100 patients are estimated to provide the required number of 1117 patients with a primary event during an anticipated recruitment period of 26 months and a minimum follow-up period of 13.5 months (total study duration 39 months).

In addition, the expected number of patients who will be lost to follow-up is expected to be small; hence, these are not considered in the determination of the sample size.

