9.4.1 Efficacy analyses

9.4.1.1 Analysis of the primary variable

The primary variable is the time from randomisation to first event included in the primary composite endpoint. Two hypotheses will be tested simultaneously (i.e., dual primary endpoint analyses): (1) in the full population and (2) in an LVEF <60% subpopulation, with alpha allocated to each test. The primary analysis will be based on the ITT principle using the FAS, including events occurring on or prior to the PACD, adjudicated by the CEA committee.

In the analysis of the primary composite endpoint, treatments (dapagliflozin versus placebo) will be compared using a Cox proportional hazards model with a factor for treatment group, stratified by T2D status at randomisation. The p-value, HR and 95% confidence interval will be reported.

The contribution of each component of the primary composite endpoint to the overall treatment effect will be examined. Methods similar to those described for the primary analysis will be used to separately analyse the time from randomisation to the first occurrence of each component of the primary composite endpoint. HR and 95% confidence intervals will be reported.

Kaplan-Meier estimates of the cumulative incidence to the first occurrence of any event in the primary endpoint will be calculated and plotted, for overall analysis and for the individual components.

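### Section 9.4.1.1 labels Kaplan-Meier estimates as cumulative incidence although deaths outside the endpoint compete, so the descriptive curves run modestly too high

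*Protocol*

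**What the plan says.** Section 9.4.1.1 commits to an estimator and names the quantity it is meant to estimate: "Kaplan-Meier estimates of the cumulative incidence to the first occurrence of any event in the primary endpoint will be calculated and plotted", and this "for overall analysis and for the individual components". The same section will "separately analyse the time from randomisation to the first occurrence of each component of the primary composite endpoint" by methods similar to the primary analysis. It names no competing-risk estimator and gives no handling of non-CV death for the curves.

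The components in section 3 are CV death, hospitalisation for HF and urgent HF visit. Section 4.2 explains why non-CV death is left out: the reason for "selecting CV death over all-cause death is the expectation that HF treatment will decrease CV death and not all potential causes of death". Section 8.3.2 secures the data needed to separate the two kinds of death: "All deaths will be adjudicated to determine if they are CV or non-CV deaths".

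**The concern.** Cumulative incidence at time t is the proportion of randomised patients who have had the event by t. A patient who has died of a non-CV cause can no longer have a primary event. Kaplan-Meier treats that patient as censored and in effect passes the share on to those still at risk. 1-KM therefore estimates the risk in a setting without competing deaths. It equals the cumulative incidence only if nobody dies of a competing cause, and otherwise lies above it.

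For the composite and for CV death the competing event is non-CV death. For HF hospitalisation and urgent HF visit it is any death, CV death included, so the relative error is largest there. What is at stake is the percentage on the plotted axis and any absolute risk or risk difference read from it. Censoring competing deaths is legitimate in the Cox model, which compares cause-specific hazards, so the hazard ratios and p-values are not at issue.

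**Working it through.** **Inputs from the protocol.** Section 9.2 gives an "annual event rate of 9% in the placebo group" for most patients, a hazard ratio of 0.80, an 11% subacute share at 24% in year 1 and 9% afterwards, 6100 patients, and an "anticipated recruitment period of 26 months and a minimum follow-up period of 13.5 months".

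**Assumed, because the protocol gives no figure.** Non-CV death at 2%, 3% or 5% per year; HF events at 7% per year (range 6% to 8%); CV death at 2.4% to 4% per year. The only mortality figure is in section 2.1: all-cause, up to 15% per year in community settings.

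**The plan's own figure.** Read the 9% as an annual probability, so that the hazard is -ln(0.91) = 0.0943 per year, with -ln(0.76) = 0.2744 for subacute patients in year 1. Average 1 - exp(-cumulative hazard) over follow-up uniform on 13.5 to 39.5 months, with the hazard multiplied by 0.80 in the active arm and no competing death. This gives 1117 events from 6100 patients, which matches section 9.2. The same reading of 9% is used below, without the subacute excess.

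**Formulas** (constant event hazard h, competing hazard c):
- 1-KM = 1 - exp(-h t)
- Cumulative incidence = h/(h + c) × [1 - exp(-(h + c) t)]

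**Composite, h = 0.0943.** Example at 24 months with c = 0.02: 0.0943/0.1143 × (1 - exp(-0.2286)) = 16.86%, against 1 - exp(-0.1886) = 17.19%.

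| Months | 1-KM | Cumulative incidence, c = 0.02 / 0.03 / 0.05 | Excess, points |
|---|---|---|---|
| 24 | 17.19% | 16.86 / 16.70 / 16.38% | 0.33 / 0.49 / 0.81 |
| 36 | 24.64% | 23.95 / 23.62 / 22.96% | 0.69 / 1.03 / 1.68 |

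**HF events, h = 0.07.** This leaves 0.0943 - 0.07 = 0.0243 for CV death as first event. Adding non-CV death gives c = 0.0443, 0.0543 or 0.0743.

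| Months | 1-KM | Cumulative incidence | Excess, points |
|---|---|---|---|
| 24 | 13.06% | 12.51 / 12.40 / 12.16% | 0.55 / 0.67 / 0.90 |
| 36 | 18.94% | 17.78 / 17.53 / 17.04% | 1.16 / 1.41 / 1.90 |

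At 36 months the relative excess is 7% to 11%. With h between 0.06 and 0.08 under the same constraint, the excess stays at 1.0 to 1.9 points.

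**CV death,** h = 0.024 to 0.04, c = 0.02 to 0.05: excess 0.2 to 0.8 points at 36 months.

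**Risk difference at 36 months,** hazard ratio 0.80 on HF events and CV death, no effect on non-CV death: composite 4.39 points by 1-KM against 4.27 to 4.10; HF events 3.48 against 3.17 to 3.04.

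**How much of the trial reaches these times.** With uniform accrual, mean potential follow-up is 13.5 + 26/2 = 26.5 months. Only (39.5 - 36)/26, about 13% of patients, can reach 36 months.

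**The case against.** Nobody disputes the direction. The case against is about weight, and it has five parts.

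- **No decision uses a curve.** Superiority is judged by the stratified Cox model, and the protocol defines no absolute risk or number needed to treat to be read from a plot. This stands, and it limits the point to description.
- **The composite error is about the size of sampling noise.** With about 3050 patients per arm, the standard error of the Kaplan-Meier estimate is roughly 0.73 to 0.75 points at 24 months and 1.10 to 1.14 at 36 months. This is true, but a bias always goes one way and does not shrink with more patients.
- **The size rests on assumed rates.** At 1% non-CV death per year the composite excess is only 0.17 points at 24 months and 0.35 at 36. This also stands: the direction is certain, the size is not.
- **The HF figures merge two components that the protocol lists separately.** For urgent HF visits at an assumed 0.5% to 1% per year, the 36-month excess is only about 0.1 to 0.3 points. In relative terms it is still about 7% to 11%, so the statement that the HF components are relatively most affected holds.
- **The SAP may add competing-risk curves, and a new label would cure the mismatch.** The SAP may do so, but the protocol does not leave the matter open: it names both the quantity and the estimator. Relabelling does remove the mismatch, but the reader then has no estimate of the actual cumulative incidence.

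**Conclusion.** The concern holds. Section 9.4.1.1 pairs cumulative incidence with an estimator that overstates it whenever competing deaths occur, and the endpoint definition guarantees that some deaths compete. Under non-CV death of 2% to 5% per year, the overstatement for the composite is 0.3 to 0.8 points at 24 months and 0.7 to 1.7 at 36 months. For HF events it is 0.5 to 0.9 and 1.2 to 1.9 points. The composite risk difference at 36 months moves by at most about 0.3 points and the HF one by about 0.3 to 0.4. All rates except the 9% are assumptions, hazards are taken as constant, and 36 months is the thin tail of follow-up. Confirmatory inference is untouched. This is a modest descriptive error that should be corrected because correcting it is nearly free.

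**What to change.** Amend the last paragraph of section 9.4.1.1 to estimate and plot cumulative incidence by the Aalen-Johansen method. The competing event is non-CV death for the composite and for CV death, and death from any cause for hospitalisation for HF and for urgent HF visit. Keep the stratified Cox model for hazard ratios and tests. If a Kaplan-Meier display is kept, label it 1-KM and not cumulative incidence.

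The cost is one sentence and a standard software option. No new data are needed, because all deaths are already adjudicated as CV or non-CV. The downside is that the curves will sit slightly lower than 1-KM curves and be less directly comparable with them.

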9.4.1.2 Analysis of the secondary variables

The outcome of all HF events (first and recurring) and CV death will be analysed by the semi-parametric proportional rates model (Lin et al 2000) to test the treatment effect and to quantify the treatment difference. The rate ratio and its 95% confidence interval and corresponding two-sided p-value will be presented. This outcome will also be analysed for the LVEF <60% subpopulation within the multiple testing procedure as described in Section 9.2.

The analysis of change from baseline for KCCQ total symptom score at 8 months will be further detailed in the statistical analysis plan, e.g. with consideration of handling of patients who die. In addition to the secondary endpoint, total symptom score, the overall summary score, clinical summary score and domain scores will be analysed. A responder analysis will also be performed (more details presented in the SAP).

The analysis of the endpoints time from randomisation to CV death and time to all-cause mortality will be analysed in the similar manner as the primary variable.

9.4.1.3 Subgroup analysis

Subgroup variables for the primary efficacy endpoint include demography, baseline disease characteristics, baseline concomitant medications and others. Cox proportional hazard model stratified for T2D with factors for treatment group, the subgroup variable and the interaction between treatment and subgroup will be used to examine treatment effects within relevant subgroups separately. A test of interaction between randomised treatment group and the subgroup variable will be performed in each Cox model. The p-values for the subgroup analyses will not be adjusted for multiple comparisons as the tests are exploratory and will be interpreted descriptively. Treatment differences with 95% confidence intervals will be reported for each subgroup. HRs and CIs for overall analysis and subgroups will be presented with forest plots as well. Further details of the subgroup analysis, including the list of subgroup variables, will be provided in the SAP.

9.4.1.4 Sensitivity analysis

Details of the sensitivity analysis for the primary and secondary endpoints will be provided in the SAP.

9.4.2 Safety analyses

All safety analyses will be performed on the Safety analysis set. The number and percent of patients with SAEs, DAEs, amputations, and potential preceding events for lower limb amputations will be summarised by treatment group, and by system organ class and preferred term.

For safety analyses, summaries will be provided using both on treatment observations and using all observations regardless of whether patients are on or off study treatment.

9.4.3 Methods for multiplicity control

A closed testing procedure including a pre-specified hierarchical ordering of the primary and secondary endpoints will be utilised. The Type I error will be controlled at an overall two-sided 5% level for multiplicity across primary and secondary endpoints and in consideration of the planned interim analysis. With one interim analysis at 67% of events (see Section 9.5) the two-sided significance level in final analysis, α , will be 4.980%. Statistical significance will be assessed in two branches in a pre-specified order of the endpoints and populations which is further described in the SAP. The significance level α , will be split for the two primary analyses, denoted α_1 and α_2 . If either of the tests of the primary endpoint in the full study population and for LVEF <60% subpopulation is significant at respective levels α_1 and α_2 , the next hypothesis in the respective branch sequence will be tested at the same significance level. The exact split of alpha will be documented in an updated SAP before the interim analysis. If all hypotheses in one arm are rejected, the alpha will be recycled to the other branch.

9.5 Interim analyses

An interim analysis is planned to be performed including approximately 67% of the target number of patients with adjudicated primary endpoint events (approximately 748 events). There will in principle be one planned interim analysis for efficacy, with the possibility of the DMC to conduct subsequent interim analysis if they deem necessary. The significance level for final analysis will be determined by the Haybittle-Peto function based on the actual number of interim analyses. The interim analysis will assess superiority of dapagliflozin to placebo. The interim analysis will have a nominal two-sided alpha level of 0.2%. At the interim analysis, the primary composite endpoint will be tested in the full study population at the specified alpha level. If superiority is achieved for the primary endpoint, then the superiority of dapagliflozin to placebo on CV deaths will be tested in the full study population at a two-sided level of 0.2%. If CV death is significant, then an action is triggered whereby the DMC will evaluate the totality of the efficacy data and safety data, to determine if benefit is unequivocal and overwhelming such that the DMC recommends ending the study.

In the initial version of the protocol, there was a planned futility analysis to be performed at the time of interim analysis. This futility analysis was removed, since formal testing was updated to

include both the LVEF <60% subpopulation and full study population, and that this potentially creates complex scenarios related to futility and benefit in one, other or both populations.

9.5.1 Data monitoring committee (DMC)

An independent data monitoring committee (DMC) will be appointed and will report to the Executive Committee. The DMC will be responsible for safeguarding the interests of the patients in the outcome study by assessing the safety of the intervention during the study. The DMC will have access to the individual treatment codes and be able to merge these with the collected study data while the study is ongoing. A charter will be prepared to detail precise roles and responsibilities and procedures of the DMC.

11. SUPPORTING DOCUMENTATION AND OPERATIONAL CONSIDERATIONS

Appendix A Regulatory, ethical and study oversight considerations

A 1 Regulatory and ethical considerations

This study will be conducted in accordance with the protocol and with the following:

- Consensus ethical principles derived from international guidelines including the Declaration of Helsinki and Council for International Organizations of Medical Sciences (CIOMS) International Ethical Guidelines
- Applicable ICH Good Clinical Practice (GCP) Guidelines
- Applicable laws and regulations

The protocol, protocol amendments, ICF, Investigator Brochure, and other relevant documents (e.g. advertisements) must be submitted to an IRB/IEC by the investigator and reviewed and approved by the IRB/IEC before the study is initiated.

Any amendments to the protocol will require IRB/IEC approval before implementation of changes made to the study design, except for changes necessary to eliminate an immediate hazard to study subjects.

The investigator will be responsible for the following:

- Providing written summaries of the status of the study to the IRB/IEC annually or more frequently in accordance with the requirements, policies, and procedures established by the IRB/IEC
- Notifying the IRB/IEC of SAEs or other significant safety findings as required by IRB/IEC procedures
- Providing oversight of the conduct of the study at the site and adherence to requirements of 21 CFR, ICH guidelines, the IRB/IEC, European regulation 536/2014 for clinical studies (if applicable), and all other applicable local regulations

The study will be performed in accordance with the AstraZeneca policy on Bioethics and Human Biological Samples.

A 2 Financial disclosure

Investigators and sub-investigators will provide the sponsor with sufficient, accurate financial information as requested to allow the sponsor to submit complete and accurate financial certification or disclosure statements to the appropriate regulatory authorities. Investigators are

responsible for providing information on financial interests during the course of the study and for 1 year after completion of the study.

A 3 Informed consent process

The Investigator or his/her representative will explain the nature of the study to the subject or his/her legally authorised representative and answer all questions regarding the study.

Subjects must be informed that their participation is voluntary. Subjects or their legally authorised representative will be required to sign a statement of informed consent that meets the requirements of 21 CFR 50, local regulations, ICH guidelines, Health Insurance Portability and Accountability Act (HIPAA) requirements, where applicable, and the IRB/IEC or study centre.

The medical record must include a statement that written informed consent was obtained before the subject was enrolled in the study and the date the written consent was obtained. The authorised person obtaining the informed consent must also sign the ICF.

Subjects must be re-consented to the most current version of the ICF(s) during their participation in the study.

A copy of the ICF(s) must be provided to the subject or the subject's legally authorised representative.

A subject who is rescreened is required to sign another ICF.

A 4 Data protection

Each subject will be assigned a unique identifier by the sponsor. Any subject records or data sets transferred to the sponsor will contain only the identifier; subject names or any information which would make the subject identifiable will not be transferred.

The subject must be informed that his/her personal study- related data will be used by the sponsor in accordance with local data protection law. The level of disclosure must also be explained to the subject.

The subject must be informed that his/her medical records may be examined by Clinical Quality Assurance auditors or other authorised personnel appointed by the sponsor, by appropriate IRB/IEC members, and by inspectors from regulatory authorities.

A 5 Committees structure

Executive Committee

Together with AZ, the Executive Committee will be responsible for the final overall study design, including the development of the study protocol and eCRF, supervision of the study conduct and progress, development of any protocol amendments needed during the study, liaison with the CEA committee and DMC committee as needed, development of the statistical analysis plan,

interpretation of the final data and reporting (presentations at international congresses and publications in peer reviewed journals) of the study.

The Executive Committee will make recommendations to AstraZeneca with regards to early stopping or modifications of the study based on the information received from the DMC. The Executive Committee will be comprised of designated international academic leaders and nonvoting members of the Sponsor, and will operate under an Executive Committee charter.

National Lead Investigator (NLI) Committee

The National Lead Investigator (NLI) Committee will be comprised of NLIs from each country where the study is conducted and supervised by the Executive Committee. Members of the committee will be responsible for providing clinical guidance on study implementation, recruitment and study conduct in their respective country.

Data Monitoring Committee (DMC)

An independent DMC will be appointed and will report to the Executive Committee. The DMC will be responsible for safeguarding the interests of the patients in the outcome study by assessing the safety of the intervention during the study, and for reviewing the overall conduct of the study. The DMC will have access to the individual treatment codes and be able to merge these with the collected study data while the study is ongoing. A DMC charter will be prepared to detail precise roles and responsibilities and procedures to ensure maintenance of the blinding and integrity of the study in the review of accumulating data and interactions with the Executive Committee.

Clinical Event Adjudication (CEA) Committee

The role of the CEA committee is to independently review, interpret and adjudicate potential endpoints that are experienced by the patients. Endpoints will be identified preliminary by the investigators, and also by AZ personnel or in the CEA process as specified in the CEA charter. The CEA committee members will not have access to individual treatment codes for any patient or clinical efficacy endpoint and safety event. The precise responsibilities and procedures applicable for CEA will be detailed in the CEA charter.

A 6 Dissemination of clinical study data

A description of this clinical trial will be available on <http://astrazenecaclinicaltrials.com> and <http://www.clinicaltrials.gov> as will the summary of the main study results when they are available. The clinical trial and/or summary of main study results may also be available on other websites according to the regulations of the countries in which the main study is conducted.

A 7 Data quality assurance

All subject data relating to the study will be recorded on printed or electronic CRF unless transmitted to the sponsor or designee electronically (e.g. laboratory data). The Investigator is responsible for verifying that data entries are accurate and correct by physically or electronically signing the CRF.

The Investigator must maintain accurate documentation (source data) that supports the information entered in the CRF.

The Investigator must permit study-related monitoring, audits, IRB/IEC review, and regulatory agency inspections and provide direct access to source data documents.

The sponsor or designee is responsible for the data management of this study including quality checking of the data.

Study monitors will perform ongoing source data verification to confirm that data entered into the CRF by authorised site personnel are accurate, complete, and verifiable from source documents; that the safety and rights of subjects are being protected; and that the study is being conducted in accordance with the currently approved protocol and any other study agreements, ICH GCP, and all applicable regulatory requirements.

Records and documents, including signed ICFs, pertaining to the conduct of this study must be retained by the Investigator for 15 years after study completion unless local regulations or institutional policies require a longer retention period. No records may be destroyed during the retention period without the written approval of the sponsor. No records may be transferred to another location or party without written notification to the sponsor.

A 8 Source documents

Source documents provide evidence for the existence of the subject and substantiate the integrity of the data collected. Source documents are filed at the Investigator's site.

Data reported on the CRF that are transcribed from source documents must be consistent with the source documents or the discrepancies must be explained. The Investigator may need to request previous medical records or transfer records, depending on the study. Also, current medical records must be available.

A 9 Publication policy

The results of this study may be published or presented at scientific meetings. If this is foreseen, the investigator agrees to submit all manuscripts or abstracts to the sponsor before submission. This allows the sponsor to protect proprietary information and to provide comments.

The sponsor will comply with the requirements for publication of study results. In accordance with standard editorial and ethical practice, the sponsor will generally support publication of multicentre studies only in their entirety and not as individual site data. In this case, a coordinating investigator will be designated by mutual agreement.

Authorship will be determined by mutual agreement and in line with International Committee of Medical Journal Editors authorship requirements.

